- 5. Visit 4 (Telephone visit). After the subject has started the 5 mg dose of the medication in test period 1, the subject will be called 1 week after initiation of study drug. If the subject is tolerating the medication, the dose will be increased to 2 tabs (10mg). If for some reason, the subject is not tolerating the medication the subject will continue on 5 mg daily, particularly if dizziness is present. The patients will also be asked if they have had any low blood sugars and what time the low blood sugars were. The blood sugars will be relayed to the PI in case there is any hypoglycemia. The PI will then make the necessary changes to the patient's background therapy to prevent further hypoglycemia.
- 6. Visit 5 (telephone visit): Visit 5 will be a telephone visit that will occur 2 weeks after the visit 4 telephone visit. The purpose of the telephone visit is to ensure that the subject is tolerating the medication. This is particularly important if the dose had been increased to the maximum dose of 2 tablets during visit 4. The patients will also be asked if they have had any low blood sugars and what time the low blood sugars were. The blood sugars will be relayed to the PI in case there is any hypoglycemia. The PI will then make the necessary changes to the patient's background therapy to prevent further hypoglycemia.
- 7. Visit 6 (cross over visit) –Visit 6 will occur 6 weeks +/- 7 days after randomization. The subject will come in fasting for this visit. During this visit, subject will undergo a brief physical examination. Blood and urine sample will be collected and the EndoPAT procedure will be conducted. Subject will take the last dose of the first lot of medication on the day of visit 6. Subject will start the24 hr. AMBP and 24 hour urine collection on the day of visit 6 after taking the last dose of the medication for test period 1.
- 8. **Visit 7**: Next day. Return AMBP monitor and then start the washout period which will last at least 14-28 days.
- 9. Test period 2: Test period 2 will start with visit 8
- 10. Visit 8: After the washout period of 14-28 days, the subject will come to the research suite in a fasting state and undergo blood and urine sample collection. Patient will receive the second medication and enter test period 2. The subject will start the new lot of medication- dapagliflozin at 5 mg (1 tablet) or placebo. During this visit, the subject will undergo EndoPAT procedure and will be started on ABPM.

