- 11. Visit 9 (the day after visit 8): The subject will return the ABPM.
- 12. Visit 10 (telephone visit): After the subject has started the medication in test period 2, the subject will be called 1 week later. If the subject is tolerating the medication, the dose will be increased to 2 tablets daily (10 mg). If for some reason, the subject is not tolerating the medication the subject will continue on 5 mg daily, particularly if dizziness is present. The patients will also be asked if they have had any low blood sugars and what time the low blood sugars were. The blood sugars will be relayed to the PI in case there is any hypoglycemia. The PI will then make the necessary changes to the patient's background therapy to prevent further hypoglycemia.
- 13. Visit 11 (telephone visit): will be a telephone visit that will occur 2 weeks after visit 10 which is also a telephone visit. The purpose of the telephone visit is to ensure that the subject is tolerating the medication. This is particularly important if the dose had been increased to the maximum dose of 2 tablets (10 mg) during visit 7. The patients will also be asked if they have had any low blood sugars and what time the low blood sugars were. The blood sugars will be relayed to the PI in case there is any hypoglycemia. The PI will then make the necessary changes to the patient's background therapy to prevent further hypoglycemia.
- 14. Visit 12; (end of treatment visit): This visit will conclude test period 2 six weeks after the washout period. During this fasting visit, a brief physical examination will be done, blood and urine samples will be collected, and the EndoPAT procedure will be conducted. Subjects will take the last dose of the second lot of medication on the day of visit 11. Subject will start the 24 hr. AMBP and urine collection after taking the last dose of the medication for test period 2.
- 15. Visit 13: The day after visit 12, the subject will return the AMBP monitor. This concludes the study.

NOTE: In order to give patients flexibility all visit will have a window of +/-7 days for visits **Study Flow chart:**

A: For the study comparing Dapagliflozin and placebo:

Visit 12 (cross over visit- 6 weeks +/- 7 days after visit 8)

- 5- physical examination
- 6- Fasting laboratory work up

(Collection of fasting blood and urine samples)

- 7- Subject is started on ABPM. Subject takes the last dose of the medication given in test period 2
- 8- EndoPAT procedure conducted.

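### Low severity: in the dapagliflozin/placebo schedule, the Visit 12 entry dates the last period-2 dose to Visit 11, a phone call at nominal day 21, while the Visit 12 flow-chart box puts it at nominal day 42

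*Combined protocol and SAP*

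**What the plan says.** All the text below concerns the dapagliflozin/placebo crossover.

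- **Visit Schedule, Visit 12, last dose:** "Subjects will take the last dose of the second lot of medication on the day of visit 11".
- **Same entry, timing:** "This visit will conclude test period 2 six weeks after the washout period".
- **Same entry, the sentence after the last-dose instruction:** "Subject will start the 24 hr. AMBP and urine collection after taking the last dose of the medication for test period 2". The Visit 13 entry has the monitor returned the day after Visit 12.
- **Study Flow chart, Visit 12 box:** timed as "Visit 12 (cross over visit- 6 weeks +/- 7 days after visit 8", and among its steps: "Subject takes the last dose of the medication given in test period 2".
- **Visit Schedule, Visit 10:** "After the subject has started the medication in test period 2, the subject will be called 1 week later".
- **Visit Schedule, Visit 11:** this "will be a telephone visit that will occur 2 weeks after visit 10 which is also a telephone visit". Its stated purpose is to check tolerability, and it contains no instruction to stop the drug.
- **Visit Schedule, Visit 6 (end of period 1):** "Subject will take the last dose of the first lot of medication on the day of visit 6".

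Proposed Studies plans 6 weeks on each treatment, and Measurements item 1 places the ABPM before and after 6 weeks of treatment.

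**The concern.** The sentence is an operational dosing instruction. It sits in the entry for the visit that supplies the after-treatment values for period 2: urine AGT (the primary endpoint), 24-hour ABPM and EndoPAT. It ties the last tablet to a telephone call about halfway through the period, while the flow chart ties it to the end-of-treatment clinic visit. Both cannot be followed.

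If a site acted on the sentence, tablets would stop early in both sequences. For participants taking placebo in period 2, no active drug would be withdrawn. For those who had placebo first and dapagliflozin second, the values meant to show the drug's effect would be taken some weeks after the drug had stopped.

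**Working it through.** The plan gives no calculated figure to reproduce here. The check is calendar arithmetic on the protocol's own intervals, followed by a comparison of the texts.

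**Nominal days, counting Visit 8 (start of period 2) as day 0**

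| Event | Source | Calculation | Nominal day |
|---|---|---|---|
| Visit 8 | Visit Schedule | start | 0 |
| Visit 10, call | Visit Schedule | 0 + 7 | 7 |
| Visit 11, call | Visit Schedule | 7 + 14 | 21 |
| Visit 12, clinic | Visit Schedule and flow chart | 6 × 7 | 42 |

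Read literally, dosing would last 21 of 42 days (50%), and the end-of-period measurements would come 42 − 21 = 21 days after the last dose.

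**Can the ±7-day visit window reconcile the two?**

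- With each visit within 7 days of its nominal day, Visit 11 falls on days 14 to 28 and Visit 12 on days 35 to 49.
- Smallest gap: 35 − 28 = 7 days. Largest gap: 49 − 14 = 35 days.
- The gap closes only if the windows are stacked. Visit 10 would be 7 days late (day 14), Visit 11 would be 14 days after that and a further 7 days late (14 + 14 + 7 = day 35), and Visit 12 would be at its earliest (day 35).

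The window therefore does not make the sentence correct.

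**How strongly each text bears on the sentence**

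- *Flow-chart box for Visit 12:* a direct contradiction. It is the only place that states outright that the last period-2 dose is taken at Visit 12.
- *Rest of the Visit 12 entry:* a contradiction by implication. The visit closes the period at six weeks, and the recording and urine collection follow the last dose. Return of the monitor the day after Visit 12 means the 24-hour recording starts at Visit 12.
- *Six weeks per treatment (Proposed Studies, Measurements item 1):* a duration, not a dosing date, but three weeks of tablets does not meet it.
- *Visit 6 rule:* a parallel only. It governs period 1, so it supports the intended reading without conflicting with a period-2 instruction.

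**After correction:** with the last dose on the day of Visit 12, it falls on nominal day 42 (window 35 to 49). This gives six weeks of treatment and agrees with the flow chart and with the way period 1 ends.

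**The case against.** The strongest reply is that the text resolves the matter where it occurs. The entry is headed as the end-of-treatment visit, its other sentences point to Visit 12, the flow chart names the dose there, and the Visit 11 call carries no instruction to stop. Staff would probably dose correctly. There is also a plausible origin for the number. In the sulfonylurea arm, Visit 12 is the day after Visit 11, so Visit 11 appears to be the end-of-treatment visit there, and its number may have been carried across. All of this stands and is why the severity is low. It does not make the sentence right, because the sentence belongs to the dapagliflozin/placebo schedule, where Visit 11 is a phone call.

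A reader might infer more than the documents support:

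- *That the whole schedule contradicts the sentence.* Only the flow-chart box states a Visit 12 last dose. The other texts imply it or run parallel to it.
- *That only the placebo-first sequence is affected.* Literally, both sequences stop tablets early. Only the loss of active drug is confined to placebo-first.
- *That a number of participants is at risk.* The crossover total is 30, but the allocation ratio is not stated. Any count would rest on an assumed ratio and on staff following one sentence against the surrounding text.
- *That the values would be taken after a full washout.* The nominal 21-day gap lies within the 14 to 28 days given for washout, but the windowed gap of 7 to 35 days extends beyond that at both ends.
- *That the treatment effect would shrink by some amount.* The documents give no basis for a figure.

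**Conclusion.** The concern holds as a low-severity inconsistency. The last-dose sentence in the Visit 12 entry is wrong as written: it is 21 nominal days earlier than the flow chart and would halve the period-2 treatment time. The conclusion rests only on intervals stated in the protocol and does not depend on any assumption about allocation, variability or effect size.

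The consequence is conditional. Off-drug measurement of urine AGT, ABPM and EndoPAT in placebo-first participants would occur only if the sentence were followed literally, and the surrounding text makes that unlikely. The likeliest explanation is a numbering slip. A reader might take the sentence to show that the crossover design is faulty or that period 2 was meant to be shorter. The documents do not support that: the design gives six weeks per treatment, and the intent for period 2 is clear.

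**What to change.** In the last-dose sentence of the Visit 12 entry, change visit 11 to visit 12. The last dose is then taken on the day of Visit 12, before the 24-hour ABPM and urine collection begin, as at Visit 6.

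In the same edit, correct the Visit 11 entry, which refers to a dose increase at visit 7. Visit 7 is the monitor return that opens the washout; the period-2 increase is made at Visit 10. This second change is editorial and affects no dose or measurement.

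The cost is two visit numbers, with no added visits, samples or participants.

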Immortalized mouse proximal tubule cells consists of cells originating from the early segment of the mouse proximal tubule. To demonstrate the effects of high glucose on AGT expression in this cell line, mPTCs were seeded on 6-well plates at a density of 5.0×105 cells per well. Before treatment in high glucose, the cells were rinsed with PBS and treated in 1.5 mL serum-free DMEM (5 mM glucose) for 8 hours. For high glucose treatment, serum-free Dulbecco Modified Eagle's Medium (DMEM) was supplemented with glucose to a final concentration of 5 mM (control), 15 mM, or 25 mM (n = 4). The cells were incubated at 37 °C for 24 hours. After treatment, cell lysates were prepared. AGT protein was detected via western blot analysis. The results of this experiment showed that our mPTC cell line exhibits a significant increase in AGT expression under high glucose conditions (15 mM and 25 mM glucose) compared to normal glucose (5 mM glucose). To test the effects of high glucose on AGT mRNA, cells were cultured as previously described in serum-free DMEM with 5 mM or 25 mM glucose (n = 3) and incubated at 37 °C.

After 24 hours, AGT mRNA was quantified via qRT-PCR. AGT mRNA relative to GAPDH mRNA was found to be significantly higher after treatment in 25 mM glucose.

The results of these preliminary experiments demonstrate that our mPTC line exhibits very low expression of AGT under normal glucose conditions (5 mM).

The impact of treatment with an SGLT2 inhibitor on intra –renal AGT production is unknown. Additionally, it is unclear what the impact of having significant glycosuria will have on AGT production. Finally, it is important to determine if there are differential effects on AGT production between SGLT2 inhibition and other methods of improving glycemic control, such as Sulfonylurea therapy

Proposed Studies

We propose to conduct a single-center randomized, double blind, cross over study of the effect of Dapagliflozin over 6 weeks, followed by placebo over 6 weeks on the other treatment allocation (those getting placebo first will cross over to Dapagliflozin and vice versa). Treatment will be stratified according to the underlying presence or absence of hypertension.

- 1. Type 2 diabetes with hypertension and on RAAS blocking drugs with stable blood pressure on therapy for at least 30 days; n= 20
- 2. Type 2 diabetes without hypertension and not on RAAS blocking drugs n=10

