If we are unable to recruit 10 patients without hypertension we will increase the number with hypertension for a total of 30. Stratification by hypertension status will remain and is important in understanding the effect of SGLT2 inhibition in patients not on BP lowering drugs

In addition a Sulfonlyurea (SU) arm will also be included -10 patients who are on metformin and other background therapy (with the exclusion of SGLT-2 inhibitor and sulfonylurea) will be recruited. This will be an open-labeled arm. Patients will assessed at baseline. They will then receive usual care for 6 weeks. At the end of 6 weeks, patients will then undergo another assessment before being provided SU for 6 weeks. At the end of 6 weeks, patients will undergo assessment again. The aim is to determine whether any effects seen with Dapagliflozin are specific to that drug or related simply to improved glycemic control.

Inclusion criteria;

As per the current approved indications for Dapagliflozin. In addition;

- 1. Type 2 diabetes with hypertension (history of hypertension in clinical records and on medication for management of hypertension) and on RAAS blocking drugs; or
- 2. Type 2 diabetes without hypertension and not on RAAS blocking drugs
- 3. Hemoglobin A1c between 7% 10% inclusive
- 4. Background therapy for diabetes to include maximally tolerated dose of metformin.
- 5. For the dapagliflozin/placebo arm, in addition to metformin, sulfonylureas and/or insulin is allowed
- 6. Estimated glomerular filtration rate (eGFR) > = 60 ml/min
- 7. Between the ages of 18 -75
- 8. Capacity to understand and sign the informed consent.

Exclusion criteria:

- 1. Current use of Dapagliflozin or any SGLT2 inhibitor
- 2. History of intolerability to Dapagliflozin
- 3. Patients with current and past history of bladder cancer
- 4. Patients with unexplainable baseline hematuria
- 5. All current contraindications of Dapagliflozin as per the label
- 6. Severe hepatic insufficiency and/or significant abnormal liver function defined as aspartate aminotransferase (AST) >3x upper limit of normal (ULN) and/or alanine aminotransferase (ALT) >3x ULN
- 7. Total bilirubin >2.0 mg/dL (34.2 μ mol/L)
- 8. Estimated glomerular filtration rate (eGFR): <60 mL/min (calculated by Cockcroft-Gault formula)
- 9. Recent Cardiovascular Events in a patient:
- 10. Acute Coronary Syndrome (ACS) within 2 months prior to enrolment

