This is a pilot study. Data from this study can be used to derive the sample size for an adequately powered study. Exploratory data analysis: All data will be cleaned and logically checked.

Exploratory analysis will be conducted to examine the distributions of each variable by means of plots (bar charts, box plots, and normal probability plots) and goodness-of-fit test statistics. Means and percentages of baseline variables will be compared between the groups. Possible outliers will be detected. Data transformation will be used to normalize the distribution of continuous variables and to improve linearity in the linear regression analyses if needed.

Comparisons of continuous variables between groups will be performed using t-tests. Chi-square tests will be employed for comparisons between categorical data. Linear regression models will be fit to examine the association between a continuous dependent variables and possible independent co-variables. Data analyses will be performed using SAS version 9 (SAS Institute Inc., SAS/STAT User's Guide, Version 9. Cary, NC: SAS Institute Inc. 2007).

Patient Safety:

A copy of the MedWatch/AdEERs report will be faxed to AstraZeneca at the time the event is reported to the FDA. It will be the responsibility of the investigator to compile all necessary information and ensure that the FDA receives a report according to the FDA reporting requirement timelines and to ensure that these reports are also submitted to AstraZeneca at the same time. When reporting to AstraZeneca, a cover page will accompany the MedWatch/AdEERs form indicating the following:

- Investigator Sponsored Study (ISS)
- The investigator IND number assigned by the FDA
- The investigator's name and address
- The trial name/title and AstraZeneca ISS reference number

The collection of AEs should start after the signing of the informed consent. Investigative site will also indicate, either in the SAE report or the cover page, the causality of events in relation to all study medications and if the SAE is related to disease progression, as determined by the principal investigator. The site research personnel will send SAE report and accompanying cover page by way to AstraZeneca: [contact] or fax number is [contact].

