Visit 13 (the day after visit 12)

Subject returns the ABPM and 24 hour urine collection No physical exam No blood or urine collection

Protocol for the sulfonylurea arm:

Visit 7 (the day after visit 6) Subject returns the ABPM and urine No physical exam No blood or urine collection

Visit 12 (the day after visit 11)

Subject returns the ABPM and 24 hour urine collection No physical exam No blood or urine collection

Measurements:

- 1- Blood pressure will be measured as per clinical practice and we will also do a 24 hr. ambulatory blood pressure monitoring before and after 6 weeks of treatment in the Dapagliflozin/ placebo arm as well as before and 6 weeks after treatment in the Sulfonylurea/placebo arm
- 2- We will also measure vascular compliance/ endothelial function using the EndoPAT test at the same visits as the ABPM only in the Dapagliflozin/placebo arm.
- 3- Spot and 24 hour urine will be collected. Urine samples will be obtained, before and after treatment. After appropriate processing, the samples will be quickly stored at -20°C, and analyzed for concentrations of AGT, albumin, and creatinine within one week of collection as previously described. The urinary AGT concentrations and urinary albumin concentrations will be normalized by urinary creatinine concentrations. Urine creatinine will also be measured and urine AGT/ creatinine calculated to correct the AGT for volume of excretion. Plasma K, renin and AGT will be measured at these visits.
- 4- Fasting plasma glucose will be measured for the Dapagliflozin/placebo and sulfonylurea arm at the following time points: a) at baseline and end of period 1 and b) at baseline and end of period 2.

Blood and urine will be stored at -70°C, for future testing of other biomarkers of renal and cardiovascular disease.

Measurements	Timings
ABPM and 24 hour urine collection	 Dapagliflozin/Placebo arm Before randomization visit (in test period 1) At the end of test period 1 (before entering washout period) At the beginning of test period 2 At the end of test period 2 (at the end of the study)
	Sulfonylurea arm - Before usual care arm visit (ie visit 2 in test period 1)

The table below summarizes the timings of the measurements:

	 At the end of test period 1 At the end of test period 2 (at the end of the study) 		

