Fasting glucose, blood and urine samples	Dapagliflozin/placebo - At the beginning of test period 1 - Before the end of test period 1 - At the beginning of test period 2 - At the beginning of test period 2 - At the beginning of test period 2 Sulfonylurea arm - Before the usual care arm visit (in test period 1)		
	 At the end of test period 1 At the end of test period 2 (at the end of the study) 		
EndoPAT Procedure	 Dapagliflozin/placebo arm only Before randomization visit (in test period 1) At the end of test period 1 At the beginning of test period 2 At the end of test period 2 		

The **primary end point** will be reduction in urine AGT comparing the AGT before and after treatment using a paired ANOVA Test.

Exploratory endpoints will be:

- 1. Examine the relationship between change in plasma K and change in urine AGT
- 2. Examine the relationship between change in BP and change in endothelial function/vascular compliance using the EndoPAT procedure.

Depending on results of this pilot study we will plan further definitive studies of the effect of SGLT2 inhibition on urine AGT, in a study with appropriate statistical power.

Forecasted key milestones dependent on IRB/IEC approval and contracting

1.	Research Agreement executed	Feb 28, 2016
2.	Projected IRB/IEC approval	Feb 28, 2016

- 3. First Subject In Apr 29, 2016
- 4. Last Subject In (100% enrollment) Apr 30, 2017
- 5. Last Subject Last Visit (Treatment end) Jun 30, 2017
- 6. Publication Jan 30, 2018

References

- 1. McFarlane SI. In: Izzo JL, Black HR, eds. *Hypertension primer: The essentials of high blood pressure*. Lippincott Williams & Wilkins; 2003:488.
- 2. National diabetes fact sheet. 2011

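### The primary end point is a before/after change in urine AGT with no baseline adjustment; if treatments are compared on it, precision is lost and the Visit 8 baseline could bring in carry-over

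*Combined protocol and SAP*

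**What the plan says.** Proposed Studies describes a "single-center randomized, double blind, cross over study of the effect of Dapagliflozin over 6 weeks, followed by placebo over 6 weeks", with the order reversed for patients allocated to placebo first. The crossover part has 30 patients: "If we are unable to recruit 10 patients without hypertension we will increase the number with hypertension for a total of 30".

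The end-point statement that follows the timing table under Measurements says that the primary end point "will be reduction in urine AGT comparing the AGT before and after treatment using a paired ANOVA Test". It names no dapagliflozin-placebo contrast, no period or sequence term and no baseline covariate. The statistical section adds general t-tests and linear regression with possible covariates, and ties neither to the primary end point.

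The Visit Schedule provides urine at Visit 2 (before any study drug), Visit 6 (end of period 1), Visit 8 (start of period 2) and Visit 12 (end of period 2). At Visit 8, which follows a 14-28 day washout, fasting patients are to "undergo blood and urine sample collection". The timing-table row for ambulatory blood pressure and 24-hour urine also covers the second baseline: "At the end of test period 1 (before entering washout period) At the beginning of test period 2". Urinary AGT is to be normalised by urinary creatinine.

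**The concern.** Each crossover patient supplies four AGT values, a baseline and an end value in each period. A treatment comparison built on before/after reduction is a difference of two differences, so it carries the error of all four. The patient already serves as his or her own control across periods. Subtracting a separate baseline in each period can therefore add more noise than it removes.

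The Visit 8 baseline raises a second issue. In patients who take dapagliflozin first, any effect still present at Visit 8 lowers that baseline, shrinks the apparent reduction on placebo and enlarges the treatment contrast.

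Both matter with about 30 patients, and the plan intends further use of the results: "This is a pilot study. Data from this study can be used to derive the sample size for an adequately powered study". A variance estimated from change scores could make the next trial larger than it needs to be.

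**Working it through.** The plan gives no alpha, power, effect size, SD or AGT correlation, so it has no figure to reproduce beyond the 30 patients.

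**Set-up.** Let B1, Y1, B2, Y2 be the baseline and end values in periods 1 and 2. Assume Var(Y1−Y2) = Var(B1−B2) = V, and let r = corr(B1−B2, Y1−Y2). Any of the candidate analyses can be written as a sequence comparison (+1/−1) of (Y1−Y2) − b(B1−B2), with per-patient variance V(1 − 2br + b²).

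- Change scores, b = 1: 2V(1−r)
- End-of-period values alone, b = 0: V
- Adjusted for the baseline difference, b = r: V(1−r²)

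Hence adjusted/change = (1−r²)/(2(1−r)) = (1+r)/2, and end-only/change = 1/(2(1−r)).

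| r (assumed) | adjusted/change | saving | end-only/change | 30 patients on change scores equal, if adjusted |
|---|---|---|---|---|
| 0 | 0.50 | 50% | 0.50 | 15 |
| 0.5 | 0.75 | 25% | 1.00 | 22.5 |
| 0.8 | 0.90 | 10% | 2.50 | 27 |

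**Cost of estimating the slope.** Simulation with 30 patients in two sequences (20,000 runs) gave adjusted/change ratios of 0.52 at r = 0, 0.73 at r = 0.4 and 0.79 at r = 0.5. The closed forms are 0.50, 0.70 and 0.75.

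**Precision at 30 patients** (assuming total SD 1, two-sided 0.05, 80% power):

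- All correlations 0.6 (r = 0): the standard error falls from √(1.6/30) = 0.231 to 0.166, and the detectable difference from 0.67 to 0.48 SD.
- Correlation 0.8 within and 0.6 between periods, so r = (0.8−0.6)/(1−0.6) = 0.5: the standard error falls from 0.163 to 0.144, and the detectable difference from 0.47 to 0.42 SD.

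**Carry-over.** Suppose a share c of the effect remains in B2 after dapagliflozin and is gone by the end of period 2. Only one of the two sequences is affected, so the relative bias is bc/2: c/2 for change scores, rc/2 for the adjusted analysis and 0 for end values alone. At c = 0.2, change scores overstate the effect by 10%; the adjusted analysis overstates it by 0%, 5% and 8% at r = 0, 0.5 and 0.8. Simulation with an effect of −0.5 SD and a residual of −0.10 SD agrees. The bias at r = 0.4 was −0.051 (change), −0.002 (end only) and −0.022 SD (adjusted), against predictions of −0.05, 0 and −0.02.

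**The other reading.** Let p1 and p0 be the within- and between-period correlations, with r = (p1−p0)/(1−p0). With unit variance, a before/after comparison within dapagliflozin alone has per-patient variance 2(1−p1). The adjusted treatment contrast has 2(1−p0)(1−r²), which is (1+r) times as large: 1.0 at r = 0 and 1.5 at r = 0.5.

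**The case against.** The strongest reply is that the plan never says changes are compared between treatments. Read literally, the end point may be before versus after within dapagliflozin, and then nothing is saved. This stands, and the variance claim is conditional on it. On that reading the defect is that the randomised placebo period goes unused in the primary analysis.

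A reader might infer that both baselines are exposed to carry-over. They are not: the period-1 baseline at Visit 2 precedes all study drug. Only Visit 8 can be affected, materially only after dapagliflozin, and the documents hold no data showing that 14-28 days is too short.

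A reader might also take a halving of variance as the expected gain. It is the r = 0 case, where the saving comes wholly from dropping the baselines. It is not a strict bound either: a slightly negative r is possible because Visit 8 falls soon after period 1 (one serial-correlation example gave r = −0.05 and a ratio of 0.47). Nor are change scores always the worse of the simple choices, since for r > 0.5 they beat unadjusted end-of-period values.

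It is also fair to say that adjustment leaves some carry-over bias and that the regression, like change scores, loses a patient with no Visit 8 baseline. Both points shape the fix. Finally, this is a pilot without a power claim, and change scores are valid if there is no carry-over. That limits the weight of the point but does not remove an almost free improvement.

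**Conclusion.** The point holds conditionally. The primary end point is a before/after change without baseline adjustment, although the samples needed for adjustment are already scheduled. If treatments are compared on those changes, adjustment multiplies the variance by about (1+r)/2: savings of 50%, 25% and 10% at r = 0, 0.5 and 0.8, a little less at 30 patients. Carry-over bias would fall from c/2 to rc/2. This rests on equal variances of the two differences, on assumed values of r and c, and, for the bias, on the effect being gone by the end of period 2. The documents do not support a claim that carry-over is present, that the variance will be halved, or that change scores are invalid. On the within-dapagliflozin reading there is no saving; the proposed model is then of use because it supplies the placebo comparison.

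**What to change.** For the dapagliflozin/placebo part only:

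1. Make end-of-period urine AGT/creatinine the primary outcome. Regress (end of period 1 minus end of period 2) on sequence (+1 dapagliflozin first, −1 placebo first) and on (baseline of period 1 minus baseline of period 2). The sequence coefficient is the dapagliflozin-placebo effect, and the intercept absorbs the period effect.
2. Report the contrast without baselines as a sensitivity analysis. It is free of the Visit 8 bias if the effect is gone by the end of period 2, but less precise than change scores when r > 0.5.
3. State how a missing Visit 8 baseline is handled, for example by a joint likelihood model of all four values, so that patients with both end-of-period values are kept.
4. Say whether AGT comes from spot or 24-hour urine, and reconcile the timing table, which lists a 24-hour collection at the start of period 2, with the Visit 8 and 9 text, which does not mention one.

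The model should not be extended as it stands to the exploratory end points, which are relationships between changes, or to the sulfonylurea arm, which has three assessments and no separate period-2 baseline. The cost is SAP wording and one degree of freedom, with no new data.
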